Given the small sample size of these clinical trials, results related to changes in inflammatory cytokines (IL-1 β , IL-2, IL-6, IL-8, IL-10, TNF- α , and IL-12p70), gut permeability biomarkers (CD14, intestinal fatty acid binding protein) and markers of endotoxemia (LPS, LPS-binding protein) are considered preliminary, and thus our principle assessment will be measurement of effect size as *Cohen's d* statistic between XN- and placebo-treated groups at each 2-week interval compared to baseline, with the primary comparison being between baseline and week 8. We will also perform formal statistical comparisons as unpaired, 2-sided t-tests (or, if inspection of distributions indicates strong non-normality, with a non-parametric Wilcoxon signed rank test) of the means at relevant time points. The following findings will be considered evidence of possible effects: 1. Clinically and statistically significant effects for changes in cytokines of interest and/or 2. Calculation of a Cohen's d value for effect size estimation greater than 0.5 (with larger d indicating a larger potential effect size).

Assessment for overall *increases* or *decreases* in parameters of interest will be tested for linear trends of the means by linear mixed ANOVA with time point as a repeated factor. Trends will be considered significant if p<0.05 for the model overall.

Analysis of XN, its metabolites, and BAs to determine a small molecule signature of longer-term oral treatment with XN:

We will identify and quantify XN and XN-derived metabolites in plasma, stool, and urine samples. Bile acid profiles will also be determined in the stool samples. The metabolite profile data will then be used for correlation with the time-resolved gut microbiome analysis. This approach will allow us to determine links between metabolite profiles and gut microbiome compositions.

Protocol

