We will apply systems biology tools to quantify how an individual's inflammation state, as measured by calprotectin, changes over time in association with XN metabolite status and microbial taxa, their genes, gut metabolites, or BAs. To link the time dependence of inflammation to these various parameters, we will follow our prior work and construct compound Poisson generalized linear models (CPGLMs) that allow us to test for differences in temporal trends in the relative abundance of specific OTUs, genes, metabolites, or BAs as a function of various experimental parameters.²⁸ CPGLMs include a point mass at zero as well as a weighted mixture of Poisson and gamma distributions. These features enable accurate modeling of the sparse (zeroinflated) but otherwise continuous and non-normal data usually produced during microbiome and metabolome investigations.²⁸ CPGLMs also correctly account for multiple sources of variation due to different experimental parameters (e.g., XN metabolite status, inflammation state, time, and sex).²⁹ We will construct CPGLMs that model how the temporal variation of each OTU, gene, or metabolite (i.e., response variables) relates to these experimental parameters. We will adopt a stepwise approach to model construction and optimal models will be identified. Models will include interaction terms that consider co-dependencies among the experimental parameters. Random intercepts and time slopes for each individual will be included in the model to account for within-individual correlation of a response variable's abundance over time. Response variables that manifest as significantly different slopes as a function of XN metabolite status are those variables that putatively interact with XN metabolites. Related analyses of model slopes will resolve parameters that elicit dependencies with inflammation state, as well as parameters that vary

Protocol

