in accordance with the XN metabolite-inflammation interaction. We will also test models that include a lag effect between response variables and these parameters to resolve, for example, taxa whose temporal change in abundance predicts subsequent inflammation changes. We have extensive experience using GLMs and related techniques for the study of microbiome-phenotype associations.^{20,22,30} Recognizing that the proposed CPGLMs are complex and may suffer from a lack of power, we may consider an alternative approach which avoids models that attempt to accommodate the data structure through zero-inflated distributional adjustments and instead consider a compositional data analysis approach, where the data is transformed and normalized using the Aitchison simplex, normalized through e.g. centered log ratio adjustment, and followed by fitting with traditional GLMs and accounting for other covariates and covariance structures. This approach would retain higher statistical power because there no longer would be an attempt to resolve the zero-inflation problem. This approach has been shown to perform better in terms of differential expression with small sample/replicate sizes.³¹ An alternative, more well-powered approach to variable/feature selection would be to perform lasso or ridge regression via elastic net, which is known to operate well in small sample relative to large feature scenarios.

Time-resolved alterations of the gut microbiome by 16S rRNA gene sequencing and metagenomics analysis:

Microbiome data generation:

We will profile the structure and functional capacity of the microbiome using 16S rRNA and shotgun metagenomic DNA sequencing. Following our prior work, we will extract whole genomic DNA from each stool sample using a QIAGEN PowerFecal DNA kit.²⁶ We will then PCR amplify the V4V5 region of the 16S gene and sequence amplicons on an Illumina MiSeq at OSU's Center for Genome Research and Biocomputing.³² We will produce 300 bp, paired-end sequences and target a sequence depth of 50,000 reads per sample. We will also generate metagenomes from the same DNA extracts using NexteraXT library preparation and the CGRB's Illumina HiSeq 3000 (150 bp paired-end sequences). We will target a sequence depth of 15 million reads per sample, which our prior work showed was more than sufficient for resolving associations between IBD and microbiome taxonomy and functional capacity.^{28,33}

Microbiome data analysis:

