provides genome-centric resolution by integrating genome binning. The full ATLAS protocol is developed and maintained as open-source software on GitHub and is implemented in Snakemake for modular, flexible, and reproducible workflows. Individual protein sequence databases will be created based on a combined metagenome that will serve as references for paired metaproteome analysis. To complement these assemblies and produce as comprehensive an assessment of microbiome structure and functional capacity as possible, we will also conduct analyses at the level of individual, unassembled reads. Specifically, we will analyze quality-controlled metagenomes using MetaPhlan2 to measure the abundance of specific microbial taxa in each metagenome.⁴¹ We will also use ShotMAP to assign reads into KEGG Orthology groups based on homology.³³ Briefly, ShotMAP predicts coding sequences from unassembled metagenomic data using Prodigal and applies RAPsearch or DIAMOND to rapidly identify reads that show evidence of homology to KEGG Orthology groups. Our prior statistical simulations surrounding this technique highlight its accuracy and our prior applications of these tools resolved taxa and microbiome metabolic modules that predict immune activation in mouse models of IBD and flare-ups in IBD patients.^{28,33}

20b Subgroup and/or adjusted analyses.

No subgroup analyses are planned. If significant differences in disease severity (CDAI-measured) become evident between XN- and placebo-treated groups, ANCOVA will be performed for all tests of mean differences (i.e., pro-inflammatory cytokine, gut permeability and endotoxemia-related parameters), adjusting for baseline CDAI score between groups.

20c Methods for imputation and/or consideration of protocol non-adherence.

To evaluate the statistical relevance of missing data, for example when the data is absent in the control group and present in the treatment group, we will utilize a G-test.²⁵ However, with multiple comparisons comes the problem of increased likelihood of a significant result by random chance. To counter this problem, we use either the Dunn-Sidak or Bonferroni correction to adjust p-values.⁴² If the data have a linear relationship, then we use partial least squares discriminant analysis (PLS-DA) and rank the molecules by p-value in a pair-wise comparison to the control group.^{43,44}

Monitoring

21a Data monitoring

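### The longitudinal feature models are chosen stepwise and then read for significance with no allowance for the search, so the p-values that label a feature XN-related are not calibrated

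*Protocol*

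**What the plan says.** Section 20a, Longitudinal regression modeling, plans a compound Poisson GLM for every OTU, gene or metabolite. XN metabolite status, inflammation state, time and sex are given as examples of the explanatory parameters. Four statements define the method:

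- Model building: "We will adopt a stepwise approach to model construction and optimal models will be identified".
- Interactions: "Models will include interaction terms that consider co-dependencies among the experimental parameters".
- Lags: "We will also test models that include a lag effect between response variables and these parameters".
- Decision rule: "Response variables that manifest as significantly different slopes as a function of XN metabolite status are those variables that putatively interact with XN metabolites".

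The random part is fixed: "Random intercepts and time slopes for each individual will be included in the model". No hold-out, permutation or other allowance for the selection is described. The one explicit threshold in this part of section 20a, "Trends will be considered significant if p<0.05 for the model overall", belongs to the mixed ANOVA for cytokines and permeability markers, not to these models. Section 20c, which deals with missing data and non-adherence, contains a multiplicity sentence: "To counter this problem, we use either the Dunn-Sidak or Bonferroni correction to adjust p-values". It is not tied to the longitudinal models.

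**The concern.** A p-value for a slope term has its usual reference distribution if the model and the term were settled before the data were seen. Here the terms kept in each feature's model, and possibly the lag, are chosen on the same 24 to 32 participants whose data then supply the test. The chosen model may differ from one feature to the next, so the flagged features would not all have passed the same test.

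The protocol also leaves open which XN term decides. With interactions in the model, the slope can differ by XN status through XN-by-time, through XN-by-sex-by-time or through XN-by-inflammation-by-time. Reading whichever is significant gives each feature several chances.

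At stake is the list of taxa, genes and metabolites said to interact with XN, which supports hypotheses 3 and 4 and the Aim 4 model in section 7.

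**Working it through.** **Plan's own figure.** None exists. The protocol gives no false-flag rate, power or sample size for these models.

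**Inputs from the protocol.** Up to 32 randomised, and 32 x 0.75 = 24 after the 25% attrition allowed in section 14. Five sampling times (weeks 0, 2, 4, 6, 8). Random intercept and time slope. Candidates: XN status, inflammation, time and sex, with interactions and lags.

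**Assumed, because not stated.** AIC as the criterion, alpha 0.05, Gaussian responses, interactions up to third order, one lag.

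**Analytic guide.** For k independent looks at 0.05 the chance of at least one flag is 1 - 0.95^k: 5% at k = 1, 14% at k = 3, 18.5% at k = 4, 26.5% at k = 6.

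**Null simulation A.** Five visits per participant, known covariance, backward AIC respecting hierarchy, N = 24 and 32, 3,000 to 4,000 features per setting, XN status coded as arm or (3,000-feature runs) as a varying metabolite level. Share of unaffected features flagged:

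| What counts as a flag | No lag | Lagged version also tried |
|---|---|---|
| Fixed model, XN-by-time only | 5.0-5.6% | 8-10% |
| Stepwise, XN-by-time only | 5-6% | 9-12% |
| Full model without selection, any of three XN slope terms | 13-14% | not run |
| Stepwise, any of three XN slope terms | 14-16% | 25-28% |
| Stepwise, any term containing XN | 27-31% | 40-51% |

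Simulation error at 3,000 features is sqrt(0.05 x 0.95 / 3000) = 0.4 points at 5% and sqrt(0.25 x 0.75 / 3000) = 0.8 points at 25%.

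**Null simulation B.** One slope per participant and seven candidates (XN, sex, inflammation, three two-way and one three-way interaction). Four of the seven contain XN, and each stands for an XN slope term.

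| What counts as a flag | No lag | Lagged version also tried |
|---|---|---|
| Fixed model, XN term only | 4-6% | not run |
| Stepwise, XN term only | 6-9% | not run |
| Full model without selection, any of four XN terms | 15-18% | not run |
| Stepwise without hierarchy, any of four | 23-29% | 34-41% |
| Stepwise with hierarchy from the full model, any of four | 20-22% | 31-32% |
| Stepwise with hierarchy from the empty model, any of four | 6-7% | 7-8% |

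**Where the excess comes from.** In one run of B at N = 24, stepwise selection with any of four terms gave 26% and the same four terms without selection gave 17%. Of the 26 - 5 = 21 points above nominal, 17 - 5 = 12 remain with no selection (57%). At N = 32 the figures are 25% and 18%, so 13 of 20 points remain (65%). Reading several terms is the larger part. Selection adds the rest, and lag versions add more on top.

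**Would the section 20c correction repair it?** Take 1,000 unaffected, independent features (an illustrative number). Bonferroni tests each at 0.05/1000 = 0.00005. With one fixed test per feature the family-wise error is 1 - (1 - 0.00005)^1000 = 4.9%. With four independent looks per feature it is 1 - (1 - 0.00005)^4000 = 18%. The absolute number of false flags becomes small, but the stated level is still exceeded, because the correction counts features and not looks within a feature.

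**The case against.** The strongest case on the other side has five parts.

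- **The stated rule may be narrow.** It speaks of slopes differing with XN metabolite status. The protocol treats inflammation dependence and the XN-inflammation interaction as related but separate analyses, and its example of a lag model concerns taxa that precede changes in inflammation. If only the XN-by-time term is read, without lags, stepwise building costs about 1 to 4 points. This stands, and it is why the low end of the range is 5-9%.
- **The unstated details may be in the SAP.** Criterion, candidate list and threshold are properly left there, and their absence is not the point. The point is that the protocol itself fixes selection followed by testing in the selected model. A SAP that only filled in the details would keep that sequence.
- **A correction is named.** It is, with unclear scope. If applied across features it would hold the per-feature rate far below the percentages above, though still above its nominal level.
- **The work is exploratory.** Features are called putative, Aim 4 is labelled exploratory, and section 20a itself concedes that these models are complex and may lack power. This limits the consequence.
- **Testing arm instead of metabolite status would change the question.** This stands, and the fix below keeps metabolite status as the exposure.

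A reader might infer that stepwise building makes about a quarter of unaffected features look XN-related. The documents do not support that as a fixed figure. It appears only under particular assumed rules, with several XN terms counted as one flag, and most of it remains when nothing is selected.

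**Conclusion.** The concern holds in a limited form. Section 20a prescribes model selection and significance testing on the same data, feature by feature, with interactions and lag versions, and makes no allowance for the search. The resulting p-values are not calibrated, and section 20c does not correct for the search within a feature.

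The size cannot be derived from the protocol. Under the assumptions listed, unaffected features are flagged at roughly 5-9% if one XN-by-time term is read, about 14-29% if any XN-containing slope term counts (13-18% on such terms without selection), and up to about 40% or more with lag versions, against about 5% for one fixed term. Forward building from an empty model under hierarchy falls below the middle range, at 6-7%. That the same text allows rates this far apart is itself a reason to fix the model. The simulations are Gaussian, and A takes the covariance as known; zero inflation and an estimated covariance at 24 to 32 participants could move the rates.

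A reader might also infer that the Aim 4 feature list will consist mainly of selection artefacts. That would need the share of truly affected features, which is neither given nor assumed here. The supported consequence is that the exploratory lists are less reliable than their p-values suggest. No primary conclusion is affected. The change should be made, but the trial does not hinge on it.

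**What to change.** Replace the stepwise sentence in section 20a with one prespecified model for every feature: XN metabolite status as the protocol uses it, time, their interaction, sex, and the random intercept and time slope already planned. Test only the XN-status-by-time term, and control the false discovery rate across features. In the simulations, one fixed term kept the per-feature rate at about 5%.

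Optionally add arm-by-time as the randomised comparison, tested by permuting arm between participants within sex, in line with the sex-based blocks in section 16a. This supplements the metabolite-status analysis and does not replace it.

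Move the XN-inflammation interaction and the lag models into a separate family labelled exploratory. The elastic net that section 20a already names would serve, with cross-validation that keeps each participant's samples together and without unadjusted p-values from the selected model.

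The cost is a change of wording before analysis and less model building than the stepwise route. The price is fewer flagged features and less flexible modelling of interactions and lags.

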We aim to extend our preliminary findings related to potential application of XN as a therapeutic by testing its effects in a sample of human adults with CD. We will recruit 32 participants with CD, and randomize them to either 24 mg of XN plus rice protein, or a rice protein placebo for 8 weeks. The study drug will be identical to the preparation used in the Phase 1 trial that preceded this Phase 2 protocol, i.e., XN will be administered as 24 mg of a 99+% pure raw material provided by Hopsteiner USA (NY) combined with 288 mg of rice protein (California Natural Products, Lathrop, CA), 109.3 mg microcrystalline cellulose (Stauber USA, Fullerton, CA), 4.3 mg Aerosil®

Protocol

200 fumed silica (Vivion Inc., San Carlos, CA), and 4.3 mg magnesium stearate (Nitika Pharmaceutical Specialties, Maharashtra, India), and formulated into a capsule by Metagenics, Inc. (Gig Harbor, WA). XN has been combined with a rice protein carrier due to improved bioavailability.⁹

Our *primary working hypothesis* is that XN at the given dose will be safe and tolerable in adults with active CD. We will test this hypothesis by collecting blood samples at screening, baseline, and every two weeks to monitor changes in laboratory values including liver enzymes, renal function markers, and hematological markers. We anticipate very low frequency of treatment discontinuation due to adverse effects.

Our *working hypotheses* of Aims 2, 3, and the Exploratory Aim are that XN and its microbiotaderived metabolites may reduce inflammation and reduce biomarkers of barrier permeability in the inflamed gut. In order to test this hypothesis, we will collect blood, urine, and stool samples at baseline and every two weeks to monitor gut microbiome profiles and measure XN metabolite profiles. We will also measure fecal metabolome (including bile acid profiles) and lipidome profiles, as well as established fecal and plasma indicators of IBD severity, including fecal calprotectin and C-reactive protein. Because the actions of XN and its metabolites target specific abnormalities in CD, we hypothesize that the proposed studies will deliver a mechanism-based biological signature of XN exposure and its effect on CD mitigation.

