A sample size of 12 per group provides 80% power to detect a 50% difference in proportions of participants between groups by chi2 test experiencing a laboratory abnormality or adverse event at a significance threshold of α =0.05. In addition, based on our preliminary trial data for change in TNF- α , and applying a 2-sided t-test of means, n=24 allows for n=12 per arm and provides >90% power, at a significance threshold α =0.05, to detect a mean change of -0.5 =/- 0.25 pg/ml in XN-treated participants with CD, based on an estimated mean change of 0.1 +/- 0.25 pg/ml from placebo. Will we randomize up to 32 participants to allow for attrition up to 25% [resulting in a final sample of at least n=24/arm.

Based on our preliminary trial data for change in TNF- α , and applying a 2-sided t-test of means, n=24 allows for n=12 per arm and provides >90% power, at a significance threshold α =0.05, to detect a mean change of -0.5 =/- 0.25 pg/ml in XN-treated participants with CD, based on an estimated mean change of 0.1 +/- 0.25 pg/ml from placebo. Will we randomize up to 32 participants to allow for attrition up to 25% [though we had <10% attrition in our previous trial in this population] resulting in a final sample of at least n=24/arm.

15 Recruitment

Participants will be recruited from the region via posted fliers and the NUNM clinic via posted fliers and IRB-approved mailings to current patients. Members of the study team will present information about study participation to CD support and community groups and set out flyers for attendees to pick up. In addition, we will use Craigslist and social media (i.e. Facebook and Instagram) as well as the NUNM weekly newsletter. Candidates from the community would

simply respond to a dedicated study telephone line or email, and express their interest, and are then contacted by a Study Coordinator.

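### Section 20b adjusts the marker comparisons only after a significant CDAI difference, and then only for CDAI, so each marker's own baseline is never a covariate and precision is lost

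*Protocol*

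**What the plan says.** Protocol section 20b makes adjustment conditional: "If significant differences in disease severity (CDAI-measured) become evident between XN- and placebo-treated groups, ANCOVA will be performed for all tests of mean differences". It lists the outcomes concerned ("i.e., pro-inflammatory cytokine, gut permeability and endotoxemia-related parameters") and the covariate ("adjusting for baseline CDAI score between groups"). It gives no test, significance level or visit for the trigger.

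When the trigger does not fire, section 20a applies to these markers. The principal measure is Cohen's d, "at each 2-week interval compared to baseline, with the primary comparison being between baseline and week 8". The protocol then adds: "We will also perform formal statistical comparisons as unpaired, 2-sided t-tests", with a Wilcoxon test as the alternative, applied to means at relevant time points. Trends are tested by "linear mixed ANOVA with time point as a repeated factor". None of these names the marker's own baseline as a covariate.

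Section 16a blocks randomisation by biological sex; CDAI is not a randomisation factor. CDAI is a secondary outcome in Table 1 and is scored at every clinical visit in Table 2, and section 7 hypothesises that XN improves it.

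**The concern.** A significance test on baseline data is a poor way to choose an analysis model. Under valid randomisation any baseline difference is due to chance, so the test fires at its nominal rate whether or not the covariate is worth adjusting for. In a trial this small, a sizeable chance imbalance can go unflagged.

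The chosen covariate also matters. A marker's own baseline is usually its strongest available predictor, and section 6a has blood and stool collected at baseline. The rule never uses that value as a covariate, even when it fires.

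Finally, section 20b does not say when the CDAI difference has to appear. As worded, a CDAI difference arising on treatment could decide which model is used for the cytokines. What is at stake is the precision of effect estimates from 24 to 32 people, and whether the analysis is fixed before the data are seen.

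**Working it through.** **The plan's own figures.** Section 14 assumes TNF-α changes of -0.5 (XN) and 0.1 (placebo), each with SD 0.25: "n=24 allows for n=12 per arm and provides >90% power". The difference is 0.6, so d = 0.6/0.25 = 2.4. A two-sided t-test with 12 per arm then has power 99.99%, consistent with the claim. The enrolment figure also reproduces: 24/(1 - 0.25) = 32 ("We will recruit 32 participants with CD"), or 16 per arm if nobody leaves. Section 14 also mentions 24 per arm, which 32 randomised cannot supply, so 12 and 16 per arm are used here.

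**How often the trigger fires.** Assume a two-sided 5% t-test on baseline CDAI. The observed imbalance needed is t(0.975, 2n - 2) × √(2/n):
- 12 per arm: 2.074 × √(2/12) = 0.85 SD.
- 16 per arm: 2.042 × √(2/16) = 0.72 SD.

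Under randomisation this happens in about 5% of trials, so about 95% get the unadjusted analysis. Chance alone produces an imbalance above 0.5 SD in about 22% (12 per arm) or 16% (16 per arm) of trials.

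**Large-sample precision.** Let each marker have SD 1 at both visits and correlation r between baseline and week 8 (r is assumed; the protocol gives none).
- Raw week-8 value: variance 1.
- Change score: 2(1 - r).
- ANCOVA on own baseline: 1 - r².
- ANCOVA relative to change score: (1 - r²)/[2(1 - r)] = (1 + r)/2, which is 0.65, 0.75, 0.85 and 0.90 at r = 0.3, 0.5, 0.7 and 0.8.
- ANCOVA relative to raw week-8 value: 1 - r², which is 0.91, 0.75, 0.51 and 0.36.

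**Small-sample power.** Simulation with 60,000 trials per setting, normal data, 12 per arm, true effect 0.8 SD, CDAI correlated 0.3 with the marker, no sex effect, and the trigger applied to baseline CDAI:

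| r | 20b rule, change scores | 20b rule, raw week-8 means | ANCOVA, own baseline and sex |
|---|---|---|---|
| 0.3 | 35% | 46% | 48% |
| 0.5 | 46% | 46% | 56% |
| 0.7 | 67% | 46% | 72% |
| 0.8 | 84% | 46% | 86% |

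Separate runs agree within one or two points (at r = 0.5, for example, 44% to 55%). At 16 per arm against change scores the gains are 59% to 70% (r = 0.5) and 80% to 85% (r = 0.7).

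**Type I error.** With no true effect and a baseline trigger, the two-stage rule rejected in about 4.4% to 5.2% of simulated trials.

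**The case against.** Several stronger readings are tempting, and the protocol does not support them.

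- **Inflated error rate.** A reader might infer that choosing the model by a pre-test raises the false-positive rate. With a baseline trigger the simulations show about 5% or slightly less. No inflation is shown.
- **Baseline ignored altogether.** Cohen's d is taken relative to baseline, the TNF-α power calculation uses mean change, and the mixed ANOVA uses repeated visits. Baseline therefore enters as a change score in the principal measure. Only the t-test wording leaves raw means open.
- **A pre-test with only 22% to 28% power.** That is the power to detect a true population CDAI difference of 0.5 SD at 12 or 16 per arm. Randomisation rules out such a difference, so the relevant facts are the 5% firing rate and the size of observed imbalance needed.
- **A trigger meant for post-treatment CDAI.** The same sentence ends by adjusting for baseline CDAI, so a baseline trigger is probably intended. The text does not say so, and the ambiguity remains.
- **Large gains everywhere.** The (1 + r)/2 ratios are large-sample, one-covariate values. With own baseline, sex and CDAI all included at 24 participants, and CDAI and sex adding no prediction, the gain over change scores is small at r = 0.7 and absent at r = 0.8.

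Two further points are fair. At the TNF-α effect assumed in section 14, power is near 100% under any of these analyses; however, section 20a counts d above 0.5 as evidence of a possible effect, so smaller effects are in view. And covariates are often left to a statistical analysis plan. Here, though, section 20b states a definite rule and names its covariate, so the criticism is of what is written. The choice of CDAI is clinically plausible; the weakness is using it alone and conditionally.

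**Conclusion.** The point holds as a matter of precision and pre-specification. The rule leaves the marker comparisons unadjusted in about 95% of trials, never uses a marker's own baseline as a covariate, and does not fix the time of its trigger.

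The size depends on r. At 12 per arm and a 0.8 SD effect, own-baseline ANCOVA adds about 13 points of power over change scores at r = 0.3, about 10 at r = 0.5, about 5 at r = 0.7, and little beyond. Against raw week-8 means the gain is negligible at r = 0.3 and large at r = 0.7 (46% to 72%). The correlations, the 0.8 SD effect and the 5% level for the trigger are assumptions.

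The consequence is moderate. These markers are secondary or exploratory, section 20a calls their results preliminary, and the primary safety outcome is untouched.

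**What to change.** Delete the significance trigger from section 20b and replace it with wording such as: XN versus placebo comparisons of the cytokine, gut permeability and endotoxemia markers at week 8, and at the other visits, use ANCOVA on the log scale where skewed, adjusted for that marker's own baseline and for sex (the stated randomisation factor), regardless of observed baseline differences. Adjustment additionally for baseline CDAI is a pre-specified sensitivity analysis.

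Limit the change to the markers section 20b already covers, and align the t-test sentence in section 20a with it. The cost is a few lines of text and one or two degrees of freedom; it needs no new visits or samples. In the simulations, adding sex with no effect of its own cost less than half a percentage point of power at 12 per arm.
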